**ALLOB-DU1 - Clinical Study Protocol**

ALLOB-DU1_CSP	V 05	Author: [name]	February 02, 2017	Pg. 31/136
---------------	------	-------------	-------------------	------------

Besides these immunoprivileged characteristics, ALLOB® also display immunosuppressive/immunomodulatory properties against activated lymphocytes in a dose-dependent manner.

#### **1.2.3 ALLOB® in Clinical Studies**

The safety and efficacy of ALLOB® is currently evaluated in phase IIa clinical studies in delayed-union fracture, spinal interbody fusion and rescue interbody fusion.

#### **1.2.4 Justification of dose**

Preclinical studies on bone formation and bone repair models in mice have demonstrated the efficacy of ALLOB® at the doses up to  $50.10^6$  cells/ml. To balance between efficacy and safety, the concentration selected for the clinical trial is  $25.10^6$ /ml, since at the maximum injected volume (of 4 ml), this concentration still presents a safety margin of over 90x.

### **1.3 Assessment of Anticipated Benefits and Risks**

Long bone delayed-union fractures are treated with debridement of the delayed-union site and internal (or external) fixation, with or without application of allo/autogenous bone graft. Although the exact pathophysiological mechanism of delayed-union is not known, delayed-union fractures may benefit from redynamisation and/or augmentation to stimulate bone formation, and hence will benefit from the addition of an osteoconductive or osteoinductive stimulus (Wiss *et al.*, 1996). This may be contributed by the local implantation of new ex-vivo cultured cells with osteogenic potential which could replace the defective or missing osteoblastic cells and re-establish a healthy bone environment. In vitro and in vivo experiments have showed that ALLOB® cells have the ability to adhere, synthesize and mineralize new bone matrix without observable toxicity. In addition, biodistribution studies have demonstrated that after local administration (at fracture site), ALLOB® cells do not migrate in non-target organs (heart, lungs, brain, liver, spleen, and kidneys). This supports the potential benefits of the use of ALLOB® in the indication of delayed-union fracture.

#### ***ALLOB® Manufacturing***

Bone marrow starting material is harvested from healthy volunteer donors selected on medical history, physical examination, laboratory parameters and (negative viral) serology according to European directives and national regulations, and raw materials entering the manufacturing

## ALLOB-DU1 - Clinical Study Protocol

ALLOB-DU1_CSP	V 05	Author: [name]	February 02, 2017	Pg. 32/136
---------------	------	-------------	-------------------	------------

process (medium, factors...) are tested for sterility, endotoxins and mycoplasmas. ALLOB® is manufactured under strict GMP and aseptic conditions. At the end of manufacturing, ALLOB® is controlled (release tests) for quality (identity, potency and absence of immunogenicity) and microbiology (sterility, endotoxins, mycoplasmas).

*ALLOB® Toxicity and Immunotoxicity*

Long-term toxicity studies have shown that ALLOB® cells even when administered at high doses (over 50-fold the maximal proposed clinical dose) did not cause any excess morbidity or mortality, did not induce any organ toxicity or did not cause ectopic bone formation. Studies have also failed to show tumoural risks at up to 300 times the human therapeutic dose). Similarly, based on preclinical studies, ALLOB® is not expected to induce immunogenic or inflammatory responses.

*Patient Benefit*

In order to minimise the risk of patient-related treatment failure during this trial, patients will be enrolled based on a strictly controlled medical criteria including classification of the disease, potential compliance with the study protocol and follow-up as well as taking into account concomitant disease and/or treatment not compatible with the ALLOB® treatment. Additionally, patients will be tested for anti-HLA antibodies and other auto-immunity markers in order to monitor the development of immune reaction against ALLOB® or the occurrence of alloreaction.

If available treatments (bone autograft) have shown 76% and 62% of radiological healing and 77% and 81% clinical healing after 9 months respectively, these benefits are counterbalanced by a large number of serious complications (Friedlander *et al.*, 2001; Nocini *et al.*, 2003; Oakley *et al.*, 2007). The minimally invasive implantation approach of ALLOB® intends to avoid the need for open surgery, and hence the related complications. In this pilot study, the test treatment ALLOB® will be provided [REDACTED] and administered to patients as a single percutaneous administration under anaesthesia at the investigating sites.

In conclusion, taking into account these precautions, the benefit/risk ratio of ALLOB® supports the initiation of its clinical development in delayed-union fractures.

**ALLOB-DU1 - Clinical Study Protocol**

ALLOB-DU1\_CSP | V 05 | Author: [name] | February 02, 2017 | Pg. 33/136

## 2 INVESTIGATIONAL PLAN

### 2.1 General Study Design

The present study is a prospective, multicentre, open, non-controlled study to assess the safety and efficacy of allogeneic osteoblastic cells (ALLOB®) implantation in non-infected delayed-union fractures.

After signing the Informed Consent Form (ICF), enrolled patients will enter an up to 8 weeks screening period. Eligible patients (according to the eligibility criteria) will be treated by a single ALLOB® implantation into the delayed-union site. Once treated, patients will be followed up during 6 months with post-treatment assessments performed: at 2 weeks, 1, 3 and 6 months, respectively. During follow-up, non-responding patients (see below and section 3.2.3) could be considered as drop-out and undergo a rescue surgery, according to the judgment of the Investigator.

[REDACTED]

[REDACTED]

[REDACTED]

Experimental design	Prospective, multicentre, open, non-controlled Phase I/IIa study
Duration of study	6 months of follow-up
Delayed-union sites	Femur, tibia, fibula, humerus, ulna, radius
Treatment	ALLOB ®
Procedure	Implantation performed under anaesthesia
Study Timepoints	2 weeks, 1 month, 3 months and 6 months after treatment

Self-contained study

Data collection: Case Report Form (CRF)

## ALLOB-DU1 - Clinical Study Protocol

ALLOB-DU1\_CSP | V 05 | Author: [name] | February 02, 2017 | Pg. 34/136

## 2.2 Study Objectives

The primary objective is to assess the safety and efficacy of ALLOB® single percutaneous implantation in healing delayed-union fractures at the end of the study period (Month 6).

This also includes a safety and efficacy interim analysis when the 16 first assessable patients will have reached the 6 month follow-up visit.

[REDACTED]

[REDACTED]

[REDACTED]

[REDACTED]

[REDACTED]

### 2.2.1 Safety

From Visit #1 to the end of the main study period at Month 6, subjects will be systematically assessed for the potential occurrence of any AE or SAE, related to the product or related to the procedure, using patient open questionnaires, physical examination, (including vital signs), and laboratory measurements.

### 2.2.2 Efficacy

The efficacy of ALLOB® will be evaluated at 6 months and based on the percentage of treated patients not failing under treatment.

A patient will be considered as failed under a treatment if, at the end of the study period (at Month 6):

- The patient had a rescue surgery

Or

- The Global Disease Evaluation score (VAS) as perceived by the patient has not improved by at least 25% and the TUS as assessed by CT scan has not increased by at least 2 points (versus baseline).

The interim analysis will be performed on same endpoints.

ALLOB-DU1 - Clinical Study Protocol

ALLOB-DU1 CSP

V 05

Author: [name]

February 02, 2017

Pg. 35/136

## ALLOB-DU1 - Clinical Study Protocol

ALLOB-DU1_CSP	V 05	Author: [name]	February 02, 2017	Pg. 36/136
---------------	------	-------------	-------------------	------------

#### 2.2.4 Consideration for Rescue Surgery

During the study follow-up, if judged necessary, the Investigators will have the possibility to withdraw the patient from the study for a rescue treatment such as a bone autograft or any other appropriate surgical or non-surgical treatment. In this case, an early discontinuation visit will be scheduled. Reasons for rescue surgery will be documented.

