#### **2.3.2.2 *Rescue Surgery Procedure***

When judged necessary, the Principal Investigator can decide to perform a rescue surgery. The patient can be withdrawn from the study for a rescue surgical (e.g., bone autograft, allograft...) or non-surgical treatment according to the standard-of-care procedure of the investigating site.

Reason for rescue surgery, type and date will be recorded.

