### 7.2.2 Additional safety examinations and procedures

If any unclear clinical event, including symptoms, signs, or other observations or abnormalities, should occur, the Investigator, or any other physician in charge, may perform additional clinical examinations and procedures (other than outlined in this protocol), including any clinical, laboratory, imaging and/or technical testing, in order to clarify and establish the aetiology and diagnosis of this clinical event.

X-ray of the thorax and liver Ultra Sound will be performed at 6 months after treatment █ in order to confirm absence of any ectopic mineralization.

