## 8 ADVERSE EVENTS AND SERIOUS ADVERSE EVENTS

### 8.1 Definitions

#### 8.1.1 Adverse Event (AE) and Serious Adverse Event (SAE)

- An adverse event (AE) is any untoward medical occurrence in a patient or clinical investigation subject who has been administered a pharmaceutical product and/or any investigational medicinal product and which does not necessarily have a causal relationship with this treatment. An AE can therefore be any unfavourable and unintended signs (including any abnormal laboratory findings), symptoms, or disease temporally associated with the use of a medicinal product, without any judgment about causality.
- All AEs will be reported from the time a signed and dated ICF is obtained until completion of the subject's last visit.
- Events related to pre-existing conditions should be reported as AE, upon Investigator's judgement, justified by an increase in frequency or intensity of signs or symptoms.
- Adverse events will be graded with respect to intensity and classified as either serious or non-serious according to the World Health Organisation Classification

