### **8.2 Reporting of Adverse Events**

The occurrence of AE/SAE (drug- or procedure- or study-related) will be assessed by non-directive questioning of the subject since the beginning of the study at the screening visit, and each follow-up visit searching for any changes in health status (e.g., "Have any Adverse events

or Serious adverse events occurred since the last visit?"). Furthermore, AE/SAE volunteered by the patient during or between the follow-up visits, or detected through observation, physical examination (including body mass index and vital signs), laboratory testing, or other clinical procedures during the observation period will be documented. Patients will be instructed that they must immediately report any adverse events, subjective complaints, or objective changes in their well-being to the Investigator or site personnel, regardless of the perceived relationship between the event and the test product.

If it is determined that an AE/SAE has occurred, the Investigator should obtain all the information required to complete the corresponding AE or SAE Form of the CRF, and establish potential causality relationship with the product or the surgical procedure.

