#### 8.2.1 Observation period for the occurrence of AEs and SAEs

**Table 9: Observation Period for the Occurrence of AEs and SAEs**

Start of Study AE/SAE Observation Period	At ICF signature
End of Study AE/SAE Observation Period	6 months after Implantation

[REDACTED]  
[REDACTED]  
[REDACTED]  
[REDACTED]

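### A patient withdrawn at rescue has, in the visible text, no Month 6 contact for newly arising non-serious AEs or for the thorax and liver imaging, and two sections give different ends to AE observation

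*Combined protocol and SAP*

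**What the plan says.** Three sections of the protocol deal with leaving the study at rescue.

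- Section 2.1: non-responders "could be considered as drop-out and undergo a rescue surgery".
- Section 2.2.4: "the Investigators will have the possibility to withdraw the patient from the study for a rescue treatment such as a bone autograft". An early discontinuation visit follows.
- Section 2.3.2.2: "The patient can be withdrawn from the study for a rescue surgical" or non-surgical treatment.

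All three permit withdrawal; none requires it. Section 5.6 places rescue surgery from Month 3 onwards. The definitions of terms describe a withdrawn patient as one who leaves before completing the last scheduled visit.

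On safety, Section 2.2 makes Month 6 safety part of the primary objective, and Section 2.2.1 states: "From Visit #1 to the end of the main study period at Month 6, subjects will be systematically assessed". Section 7.2.2 adds: "X-ray of the thorax and liver Ultra Sound will be performed at 6 months after treatment", to rule out ectopic mineralisation. Under Section 8.2, AEs are sought by non-directive questioning at screening and at each follow-up visit; also documented are any "AE/SAE volunteered by the patient during or between the follow-up visits".

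The end of AE observation is given twice. Section 8.1.1: "All AEs will be reported from the time a signed and dated ICF is obtained until completion of the subject's last visit". Table 9 in Section 8.2.1: "6 months after Implantation".

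**The concern.** A patient withdrawn at rescue leaves before Month 6, and the Month 6 visit is the contact on which solicited AEs and the imaging depend. No visible sentence keeps that contact for such a patient or moves the imaging to the exit visit. The two AE end dates roughly agree for a patient who completes Month 6. They separate for a patient who leaves early, if the last visit is read as the exit visit, so two sites could apply different rules.

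The patients affected are not a random subset. The efficacy-based rescue rule in Section 3.2.3 selects those with less than 15% improvement in Global Disease Evaluation and less than 1 point in TUS or mRUS. They stay in the safety population (Section 10.1), and so in the denominator of the AE percentages (Section 10.5.7.1), although part of their observation time may be missing.

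The protocol is explicit for comparable groups. Patients who become pregnant stay in safety follow-up (Section 8.4.1), and patients lost to follow-up are actively sought so that AEs can be established (Section 9.1). No matching rule for rescued patients is visible.

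**Working it through.** **1. What is secured after withdrawal at rescue, in the visible text**

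| Item | Covered? | Where |
|---|---|---|
| SAEs | Yes, to 24 months after end of study | 8.3.1.2 |
| AEs still open at exit | Yes, until outcome is known | 8.3, 8.3.1.1 |
| Exit caused by a possibly related AE | Yes, further examinations | 9.2 |
| New non-serious AEs, volunteered | Possibly; patients are told to report | 8.2 |
| New non-serious AEs, solicited | No visible contact after exit | 8.2 |
| Thorax X-ray, liver ultrasound | No visible rule for early leavers | 7.2.2 |

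**2. Gap between the two AE end dates**

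Visit #5 is at week 12 ± 2 and Visit #6 at week 24 ± 3. For a patient leaving at Visit #5 the gap is 24 − 12 = 12 weeks, half of the 24-week period. The visit windows give a range from (24 − 3) − (12 + 2) = 7 to (24 + 3) − (12 − 2) = 17 weeks.

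**3. Size of the possible loss**

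The protocol gives no rescue rate, so there is no figure of its own to reproduce. Assumptions, for scale only:

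- 32 treated patients, the planned maximum.
- 10% or 30% withdrawn at rescue, that is 3 or 10 patients. The 10% borrows the size of the protocol's drop-out allowance, which links 35 enrolled to 32 treated and is not a post-treatment withdrawal rate. The 30% is purely assumed.
- All withdrawals at week 12.

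*Imaging.* With no case seen among n imaged patients, the exact two-sided 95% upper limit is 1 − 0.025^(1/n):

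- n = 32: 10.9%
- n = 29: 11.9%
- n = 22: 15.4%

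*Unrecorded non-serious AEs.* Let p be the true 24-week proportion of patients with at least one such AE, at a constant rate. The 12-week proportion is h = 1 − (1 − p)^0.5. With w patients withdrawn, the reported proportion is ((32 − w)p + wh)/32, and the expected number of patients unrecorded is w(p − h).

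| p | h | w | Reported | Patients unrecorded |
|---|---|---|---|---|
| 27.0% | 14.56% | 3 | 25.8% | 0.37 |
| 27.0% | 14.56% | 10 | 23.1% | 1.24 |
| 10.0% | 5.13% | 3 | 9.5% | 0.15 |
| 10.0% | 5.13% | 10 | 8.5% | 0.49 |

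The 27.0% is the non-serious total in Table 11 for the sponsor's autologous product, used only as an illustration. The 10.0% is assumed. For a given p these are upper cases: AEs of implantation cluster early, and some later AEs would be volunteered.

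**The case against.** **Redaction.** A reader might infer that the plan has no Month 6 safety follow-up for rescued patients. The documents do not support that. The exit-visit label in Section 9.2, the Visit #6 procedure list, the schedule tables, Table 6, the lines after Table 9, a word after the imaging time in Section 7.2.2, and the post-study Sections 4.8 and 5.8 are redacted or not shown. Any of them could cover these patients; the exit visit may, for example, repeat the Visit #6 procedures. This objection stands and limits the point to the visible text. It does not remove the permission to withdraw or the two differing end dates.

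**The text already reaches Month 6.** Section 2.2.1 and Table 9 make no exception for rescue, and withdrawal is optional. This is true, but neither supplies a contact for a patient who has left.

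**Informative loss is not shown.** Rescue is linked to poor efficacy. Nothing in the documents links non-response to non-serious AEs or to ectopic mineralisation. This stands: a reader might infer biased AE rates, but only possible under-recording is supported. Missing imaging would also be visible, because missing counts are presented (Section 10.5.1.1) and discontinuations are tabulated with reasons (Section 10.5.1.3).

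**The size is negligible.** The exact 95% interval for 9 of 32 patients is 13.7% to 46.7%, so a shift from 27.0% to 25.8% or 23.1% lies well inside it. This stands.

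**Withdrawal serves efficacy.** A reader might infer that withdrawal at rescue has no role in the efficacy analysis. That holds for rescue surgery, which Section 2.2.2 already counts as failure. It does not hold for non-surgical rescue, which in the visible text becomes a failure only through the rule in Section 9.1 on early discontinuation for lack of efficacy. Keeping such patients in the study without a replacement rule would open a gap, so the fix must supply one.

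**Ending at rescue is defensible.** Section 10.5.5 ends exposure at the last visit or at rescue surgery, and autograft brings its own complications. This is a fair reason to separate AEs after rescue, but not to stop collecting them.

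**Conclusion.** The point holds as a modest one. The protocol permits, without requiring, withdrawal at rescue. In the visible text a patient so withdrawn has no Month 6 contact for solicited new non-serious AEs or for the 6-month imaging. Sections 8.1.1 and 8.2.1 can give AE end dates about 12 weeks apart for that patient, if the last visit means the exit visit; if it includes post-study visits, the difference narrows or reverses.

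The expected effect is small: roughly 0.4 to 1.2 of 32 patients with an unrecorded non-serious AE, and an imaging upper limit of 11.9% to 15.4% instead of 10.9%. Both ranges rest on assumed withdrawal of 3 or 10 patients, all at week 12, and the first also on a borrowed AE rate. Confidence is medium because of the redactions. This is a low-cost improvement and does not threaten the trial's conclusions.

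**What to change.** In Sections 2.1, 2.2.4, 2.3.2.2, 9.1 and 9.2, state that:

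- any rescue for lack of efficacy, surgical or non-surgical, is recorded as treatment failure at the time of rescue, and later values are not used for efficacy. This keeps the failure rules of Sections 2.2.2 and 9.1 in force;
- rescue does not end safety follow-up. The patient attends the scheduled Month 6 visit for AE questioning, thorax X-ray and liver ultrasound unless consent is withdrawn.

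Align Section 8.1.1 with Table 9, so that AE observation ends 6 months from implantation for every treated patient. Tabulate AEs before and after rescue separately. The decision to rescue and the choice of procedure stay with the investigator.

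The cost is amendment wording and, since rescue surgery starts from Month 3, normally one already planned visit per rescued patient. The drawback is that AEs after rescue will include complications of the rescue procedure. Section 1.1.6 cites major complications in at least 10% of autograft patients, which blurs attribution in an uncontrolled study; the before/after split limits this. If the redacted text already keeps rescued patients in follow-up, aligning the two end dates is still worth doing and costs almost nothing.

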### 2.3 Main Study Procedures

#### 2.3.1 Patient Information and Informed Consent

Before any study-related procedure, the Principal Investigator (or a member of the investigating team, designated by the Principal Investigator) will give detailed and comprehensive information regarding all aspects of the trial to the patient (or, when the patient is not capable of giving informed consent, his/her legal representative), including notably the following points:

- Purpose, objectives, and nature of the trial (including all performed procedures)
- Conditions under which the trial are conducted
- Consequences and significance of the trial
- Expected benefits
- Inconveniences and risks
- Tests performed
- Right to receive the results of the tests performed
- Rights of the patient to physical, mental, and social integrity, dignity, privacy, confidentiality, and protection of his personal data and medical records, in accordance with the Declaration of Helsinki on Ethical Principles for Medical Research involving Human Subjects, adopted by the General Assembly of the World Medical Association (1996), with amendments, and any other applicable Community and national laws, regulations, guidance, guidelines, and principles (see reference documents in Section 12)
- Medical confidentiality - recording and protection of patient data

## ALLOB-DU1 - Clinical Study Protocol

ALLOB-DU1_CSP	V 05	Author: [name]	February 02, 2017	Pg. 37/136
---------------	------	-------------	-------------------	------------

- Access and scrutiny of personal data and information during inspection by the Competent Authorities and any other properly authorized persons, provided that such information is treated as strictly confidential and is not made publicly available
- Right to refuse to participate or withdraw from the clinical trial, at any time, without any resulting detriment, penalty or loss of benefits to which the patient is otherwise entitled, notably in terms of medical care, follow-up, and patient-physician relationship
- Provision made for insurance or indemnity to cover the liability of both the Sponsor and Investigator (including all members of the investigating team and any other participants to the trial)

This detailed information will be given in both oral and written forms (Subject Information Sheet and Informed Consent Form (ICF)), in appropriate and clear manner, worded in the patient's mother tongue, using non-technical and practical language and terms that are easily understood by the patient (or his/her legal representative). The information provided will not include any term or sentence that appears to waive any of the patient's legal rights, or appears to release the Investigator, Institution/Investigating Site, Sponsor, representatives of the Sponsor, and/or the Monitor from liability for negligence.

The patient (or his/her legal representative) will then be provided sufficient time (as needed) and opportunity to inquire about details and ask any questions about the trial to the Principal Investigator (or the person who conducts the Informed Consent discussion), and to decide whether or not to participate to the trial. All questions about the trial will be answered to the satisfaction of the patient (or his/her legal representative).

If the patient (or her/his legal representative) agrees to participate, he/she will be invited to date and sign the ICF. The Principal Investigator (or the person who conducted the Informed Consent discussion) will also sign and date the document on the same day.

One original copy of the ICF signed by the patient (or her/his legal representative) and the Principal Investigator (or the person who conducted the Informed Consent discussion) will be given to the patient (or his/her legal representative), the other original duly signed copy will be kept in the Investigator's Site File at the Investigating Site.

